7.2 Chemotherapy post-apheresis

Chemotherapy will be allowed as a bridging therapy after apheresis at the provider's discretion while the CAR T cells are being manufactured. Chemotherapy immediately prior to infusion of CAR-T cells for conditioning regimen (lymphodepleting) will be standard of care at the provider's discretion.

7.3 Tisagenlecleucel Infusion

CAR-T infusion will be administered per the standard-of-care protocol at Winship Cancer Institute. Patients will remain hospitalized per the standard of care and adverse reactions (neurotoxicity, CRS) will be managed per the standard of care.

7.4 Post-Tisagenlecleucel Monitoring

Following, discharge from the hospital patients will be followed per routine practice for CAR-T patients in the clinic or in-patient hospital services. Data on performance status, vital signs, clinical exam and any history of adverse events will be captured by chart review of clinical notes on days 7,14, 28, 42 and 90 post CAR-T (section 1.2, Table 2). Blood samples will be drawn on days 7,14, 28, 42 and 90 post CAR-T draws hematology tests and the presence of CAR-T 19 cells with PCR and flow cytometry.

8. Measurement of Effect

8.1 RECIST Criteria v 1.1

Although response is not the primary endpoint of this trial, patients with measurable disease will be assessed by RECIST criteria. For the purposes of this study, patients will be re-evaluated at 3 months post CAR-T 19 infusion in comparison to a baseline scan.

8.1.1 Definitions

Evaluable for objective response. Only those patients who have measurable disease present at baseline, have received one infusion of CAR T 19 therapy, and have had their disease re-evaluated will be considered evaluable for response at 3 months (+/- 2 weeks) post CAR-T.

These patients will have their response classified according to the definitions stated below.

(Note: Patients who exhibit objective disease progression prior to the end of CAR T infusion will also be considered evaluable.)

Evaluable Non-Target Disease Response. Patients who have lesions present at baseline that are evaluable but do not meet the definitions of measurable disease, have received at least one infusion of CAR T 19 infusion, and have had their disease re-evaluated will be considered evaluable for non-target disease. The response assessment is based on the presence, absence, or unequivocal progression of the lesions.

8.1.2. Disease Parameters:

Measurable disease. Measurable lesions are defined as those that can be accurately measured in at least one dimension (longest diameter to be recorded) as ≥ 20 mm by chest x-ray or as ≥ 10 mm with CT scan, MRI, or calipers by clinical exam. All tumor measurements must be recorded in millimeters (or decimal fractions of centimeters).

Note: Tumor lesions that are situated in a previously irradiated area might or might not be considered measurable. If the investigator thinks it appropriate to include them, the conditions under which such lesions should be considered must be defined in the protocol.

Malignant lymph nodes. To be considered pathologically enlarged and measurable, a lymph node must be ≥ 15 mm in short axis when assessed by CT scan (CT scan slice thickness recommended to be no greater than 5 mm). At baseline and in follow-up, only the short axis will be measured and followed.

Non-measurable disease. All other lesions (or sites of disease), including small lesions (longest diameter <10 mm or pathological lymph nodes with ≥ 10 to <15 mm short axis), are considered non-measurable disease. Bone lesions, ascites, pleural/pericardial effusions, lymphangitis cutis/pulmonitis, and abdominal masses (not followed by CT or MRI), are considered as non-measurable.

Note: Cystic lesions that meet the criteria for radiographically defined simple cysts should not be considered as malignant lesions (neither measurable nor non-measurable) since they are, by definition, simple cysts. 'Cystic lesions' thought to represent cystic metastases can be considered as measurable lesions, if they meet the definition of measurability described above. However, if non-cystic lesions are present in the same patient, these are preferred for selection as target lesions.

8.1.3. Methods for Evaluation of Measurable Disease:

All measurements should be taken and recorded in metric notation using a ruler or calipers. All baseline evaluations should be performed as closely as possible to the beginning of treatment and never more than 4 weeks before the beginning of the treatment.

The same method of assessment and the same technique should be used to characterize each identified and reported lesion at baseline and during follow-up. Imaging-based evaluation is preferred to evaluation by clinical examination unless the lesion(s) being followed cannot be imaged but are assessable by clinical exam.

Conventional CT:

This guideline has defined measurability of lesions on CT scan based on the assumption that CT slice thickness is 5 mm or less. If CT scans have slice thickness greater than 5 mm, the minimum size for a measurable lesion should be twice the slice thickness.

Ideally, the same type of scanner should be used and the image acquisition protocol should be followed as closely as possible to prior scans. Body scans should be performed with breath-hold scanning techniques, if possible.

FDG-PET:

While FDG-PET response assessments need additional study, it is sometimes reasonable to incorporate the use of FDG-PET scanning to complement CT scanning in assessment of progression (particularly possible 'new' disease). New lesions on the basis of FDG-PET imaging can be identified according to the following algorithm:

- a. Negative FDG-PET at baseline, with a positive FDG-PET at follow-up is a sign of PD based on a new lesion.
- b. No FDG-PET at baseline and a positive FDG-PET at follow-up: If the positive FDG-PET at follow-up corresponds to a new site of disease confirmed by CT, this is PD. If the positive FDG-PET at follow-up is not confirmed as a new site of disease on CT, additional follow-up CT scans are needed to determine if there is truly progression occurring at that site (if so, the date of PD will be the date of the initial abnormal FDG-PET scan). If the positive FDG-PET at follow-up corresponds to a pre-existing site of disease on CT that is not progressing on the basis of the anatomic images, this is not PD.
- c. FDG-PET may be used to upgrade a response to a CR in a manner similar to a biopsy in cases where a residual radiographic abnormality is thought to represent fibrosis or scarring. The use of FDG-PET in this circumstance should be prospectively described in the protocol and supported by disease-specific medical literature for the indication. However, it must be acknowledged that both approaches may lead to false positive CR due to limitations of FDG-PET and biopsy resolution/sensitivity.

Note: A 'positive' FDG-PET scan lesion means one which is FDG avid with an uptake greater than twice that of the surrounding tissue on the attenuation corrected image.

8.2 Evaluation of Disease:

Complete Response (CR): Disappearance of all target lesions. Any pathological lymph nodes (whether target or non-target) must have reduction in short axis to <10 mm.

Partial Response (PR): At least a 30% decrease in the sum of the diameters of target lesions, taking as reference the baseline sum diameters.

Progressive Disease (PD): At least a 20% increase in the sum of the diameters of target lesions, taking as reference the smallest sum on study (this includes the baseline sum if that is the smallest on study). In addition to the relative increase of 20%, the sum must also demonstrate an absolute increase of at least 5 mm. (Note: the appearance of one or more new lesions is also considered progressions).

Stable Disease (SD): Neither sufficient shrinkage to qualify for PR nor sufficient increase to qualify for PD, taking as reference the smallest sum diameters while on study.

8.3 Evaluation of Best Overall Response:

The best overall response is the best response recorded from the start of the treatment until repeat imaging at 90 days. The patient's best response assignment will depend on the achievement of both measurement and confirmation criteria.

Target Lesions	Non-Target Lesions	New Lesions	Overall Response	Best Overall Response when Confirmation is Required*
CR	CR	No	CR	>4 wks. Confirmation**
CR	Non-CR/Non-PD	No	PR	>4 wks. Confirmation**
CR	Not evaluated	No	PR	
PR	Non-CR/Non-PD/not evaluated	No	PR	Documented at least once >4 wks. from baseline**
SD	Non-CR/Non-PD/not evaluated	No	SD	
PD	Any	Yes or No	PD	no prior SD, PR or CR
Any	PD***	Yes or No	PD	
Any	Any	Yes	PD	

* See RECIST 1.1 manuscript for further details on what is evidence of a new lesion.
** Only for non-randomized trials with response as primary endpoint.
*** In exceptional circumstances, unequivocal progression in non-target lesions may be accepted as disease progression.

Note: Patients with a global deterioration of health status requiring discontinuation of treatment without objective evidence of disease progression at that time should be reported as "symptomatic deterioration." Every effort should be made to document the objective progression even after discontinuation of treatment.

8.4. Assessment of Engraftment:

Molecular studies (CAR-T 19 PCR) and immune phenotyping will be collected per the study protocol procedure. All samples will be processed by the Winship Cancer Institute Laboratory.

9. Sharing of Results with Patients

In general, study staff will not provide any individual results to patients (ex. outcome trial results or results from patient's samples studies). If something of urgent medical importance to the participating patients are found, the PI (or co-Is) will inform the patient, although we expect that this will be a very rare occurrence. Samples and data will only be used for research.

10. Study Timelines

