7.1 Apheresis Collection

Patients will need to undergo leukapheresis within two (2) days of completion of the 8 to 15 day treatment of duvelisib. Apheresis will be performed at the Emory Center for Transplantation and Cell Therapy. Peripheral blood mononuclear cells will be collected for CAR-T cell manufacturing according to the standard of care. A single 2-4-hour leukapheresis will be performed on the COBE Optia with the intention of harvesting 3×10^9 white blood cells. If patients are unable to collect the necessary amount required for manufacturing, they can undergo a second leukapheresis. If patients are not able to collect enough product after the second leukapheresis, they will be considered unevaluable and replaced. After apheresis, the quantity of CD27/CD28 double positive T cells, CD4/CD8 double negative gamma delta positive T cells and CD4/CD8 double negative gamma delta negative T cells will be measured via flow cytometry. CAR-T cell manufacturing will be provided by Novartis and are expected to be ready 4 weeks after collection. Failure of the incoming apheresis material or outgoing product to meet the commercial specifications will be discussed with Novartis on a case by case basis.

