17.5.1 Study Design Endpoints

This is pilot study to examine if exposure to a dual PI3K delta and gamma inhibitor before CAR T cell leukapheresis leads to decreases in manufacturing time and enhanced expression of CD27/CD28+ T cells. Patients who receive at least 75% (23/28 doses) of duvelisib will be evaluable for final analysis. Patients who do not receive 75% of doses will be considered unevaluable and replaced. Patients who do not undergo leukapheresis within two (2) days of completion of the 8 to 15 days of duvelisib will be considered unevaluable and replaced. All patients with any exposure to duvelisib will be evaluable for toxicity (please see section 13.3 on grading of toxicities).

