17.5.3 Analysis of Secondary Endpoints

- 1). Descriptive statistics will be used to calculate the proportion of patients that completed at least 75% of duvelisib doses as documented by the patient pill diaries. The proportion along with an exact 95% confidence interval will be reported.
- 2). Descriptive statistics will be used to calculate the median manufacturing time from the 10 patients that completed at least 75% of duvelisib doses. The median will be reported along with the minimum and maximum manufacturing times.
- 3). A Wilcoxon signed-rank test will evaluate the change in proportion of CD27+/CD28+ and CD4-/CD8- T cells at baseline and at day 15
- 4). Descriptive statistics will be used to calculate the *in vivo* expansion and persistence of CAR-T 19 cells post infusion as measured by serial CAR-T 19 PCR measurements.
- 5). The ORR (complete response or partial response) will be summarized along with an exact 95% confidence interval. Disease response will be based on the RECIST criteria (version 1.1). Please see section 8.2 on the definitions of disease response.

6). The 90 day PFS and OS will be estimated using the Kaplan-Meier method and calculated with corresponding 95% confidence intervals. Please see section 8.3 on the definitions of progressive disease.

7). Descriptive statistics will be used to calculate the frequency of ICU transfers due to CRS and/or neurotoxicity. Descriptive statistics will also be used to calculate the frequency of administration of tocilizumab and/or corticosteroids use for CRS and/or neurotoxicity.

8). Descriptive statistics will be used to assess the frequency of all grade toxicities as defined by CTCAE (version 5.0).

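### The plan's only response-evaluable set leaves out infused patients with no documented re-evaluation, so the reported ORR is likely, though not certain, to read too high

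*Combined protocol and SAP*

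**What the plan says.** Section 8.1.1 sets three conditions for objective response: measurable disease at baseline, one CAR-T infusion, and re-evaluation of disease. It is worded as an exclusive restriction. Only patients meeting the first two conditions who also "have had their disease re-evaluated will be considered evaluable for response at 3 months (+/- 2 weeks) post CAR-T" are included. A note adds one group: "Patients who exhibit objective disease progression prior to the end of CAR T infusion will also be considered evaluable". The parallel set for patients with only non-target lesions carries the same condition, since they must "have had their disease re-evaluated will be considered evaluable for non-target disease".

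Section 17.5.3 item 5 gives the analysis: "The ORR (complete response or partial response) will be summarized along with an exact 95% confidence interval". It names RECIST 1.1 and points to Section 8.2 for the response definitions. It states no denominator and no rule for a missing assessment.

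Other evaluability rules exist, but they concern earlier steps. Section 17.5.1 has a dose rule ("Patients who receive at least 75% (23/28 doses) of duvelisib will be evaluable for final analysis") and replaces late collections ("Patients who do not undergo leukapheresis within two (2) days of completion"). Section 7.1 has a collection rule ("If patients are not able to collect enough product after the second leukapheresis, they will be considered unevaluable and replaced"). None of them deals with an infused patient whose response was never assessed.

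On follow-up, Table 2 and Section 5.6 schedule one post-infusion scan, at Day 90. Section 10.2 lists the 90-day radiologic assessment under patients who have not begun a new antineoplastic regimen. The note under the response table in Section 8.3 foresees patients who decline without objective progression, to be recorded as symptomatic deterioration, and adds: "Every effort should be made to document the objective progression even after discontinuation of treatment".

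**The concern.** Whether a patient enters the ORR denominator depends on reaching a re-evaluation, and the ways of not reaching one after infusion are often themselves treatment failures: early death, clinical decline, or a switch to another therapy. The note in 8.1.1 rescues failures only up to the end of infusion. After that point, a failure with no documented re-evaluation is removed and not counted as a non-response.

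At stake is the accuracy of one reported proportion. With at most about 20 patients in the denominator, each one moves the estimate by several points, and the exact confidence interval that item 5 attaches to it reflects sampling error only, not selective omission. In a single-arm study the rate is also likely to be read beside the 71% to 100% range that the background section cites.

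**Working it through.** **No planned figure to reproduce.** The documents give no target ORR, no power for ORR and no expected number of missed assessments. The 20 patients are an estimation sample for the fold change in CD27/CD28 T cells (Section 17.5.2). The figures below are therefore illustrations.

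**Inputs.** From the documents: N = 20 planned patients; ORR = CR + PR with an exact 95% CI. Assumed: all 20 are infused and have measurable disease; x respond; m have no documented re-evaluation.

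**Formulas.** Under 8.1.1, ORR = x/(N − m). With unassessed patients counted as non-responders, ORR = x/N. If all m are non-responders, the ratio of the two is N/(N − m): 20/19 = 1.05, 20/18 = 1.11 and 20/16 = 1.25 for m = 1, 2 and 4. The exact (Clopper-Pearson) limits for x of n are the 2.5% quantile of Beta(x, n − x + 1) and the 97.5% quantile of Beta(x + 1, n − x).

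**Result for x = 10, all lost patients non-responders:**

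| Unassessed (m) | ORR under 8.1.1 | Exact 95% CI | Shift from 10/20 |
|---|---|---|---|
| 0 | 10/20 = 50.0% | 27.2-72.8 | 0 |
| 1 | 10/19 = 52.6% | 28.9-75.6 | +2.6 points |
| 2 | 10/18 = 55.6% | 30.8-78.5 | +5.6 points |
| 4 | 10/16 = 62.5% | 35.4-84.8 | +12.5 points |

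**Other responder counts.** The shifts for m = 1, 2 and 4 are +1.6, +3.3 and +7.5 points with 6 responders; +2.1, +4.4 and +10.0 with 8; +3.2, +6.7 and +15.0 with 12; and +3.7, +7.8 and +17.5 with 14.

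**Does the sign depend on the lost patients all being failures?** Let p be the rate among assessed patients and q the true rate among the unassessed. The bias is p − [(N − m)p + mq]/N = (m/N)(p − q). It is upward whenever q < p, zero when q = p, and downward when q > p. Take 10 responders among 16 assessed (p = 62.5%), with m = 4 and m/N = 0.2:

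- q = 0%: 0.2 × 62.5 = +12.5 points (true rate 50.0%)
- q = 25%: 0.2 × 37.5 = +7.5 points (true rate 55.0%)
- q = 50%: 0.2 × 12.5 = +2.5 points (true rate 60.0%)
- q = 100%: 0.2 × (−37.5) = −7.5 points (true rate 70.0%)

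**Which sign is more plausible?** A switch to new therapy takes the patient outside the group for whom Section 10.2 lists the 90-day scan. Death before Day 90 prevents it. Symptomatic deterioration, as Section 8.3 describes it, comes without objective progression and is given no response category. These routes all favour q < p. A responder who simply misses the visit works the other way.

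**The case against.** The strongest reply is that 8.1.1 excludes on absence of re-evaluation, not on outcome, so the direction of bias is inferred. That is correct. A reader might infer that the dropped patients are mostly failures and that the bias is certainly upward. The documents say neither, and the last line of the sign check shows that the error can reverse. What they support is a likely direction.

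Second, 8.1.1 may not be the ORR denominator at all: item 5 cites Section 8.2, not 8.1.1, and the rule in 17.5.1 could be read as covering every endpoint except toxicity. This also stands in part. 8.1.1 governs only by default. Yet the 17.5.1 reading would not help, because that rule is silent on missing response assessments.

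Third, the group lost is narrow. Section 8.1.2 accepts caliper measurement at clinical examination, 7.4 collects examination findings by chart review on Days 7, 14, 28, 42 and 90, and progression on an unscheduled scan is a re-evaluation. The note in 8.3 also asks sites to try to document progression. All this reduces m. It does not assign an outcome to the patients who remain undocumented.

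A reader might also infer that 90-day PFS is biased by the single scan. That needs progression to be dated to the scan and the Kaplan-Meier curve to be read at exactly Day 90. The plan does not fix these two premises, so the inference is not supported.

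Finally, evaluable-only response rates have a place, and Section 8.1 says that response is not the primary endpoint. Both are true. They bear on how much this matters, not on whether the denominator should be stated.

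**Conclusion.** The concern holds in this form: no section counts an infused, unassessed patient as a non-responder, and the only response-evaluable set in the plan leaves such patients out. The reported ORR is likely, though not certain, to be too high. The size cannot be derived from the documents. Under the assumptions above (20 infused, all measurable, all unassessed patients non-responders), two unassessed patients add 3.3 to 7.8 points across 6 to 14 responders, and with none unassessed there is no bias. For comparison, the exact interval around 10/20 is about 27% to 73%, so a shift from one or two patients is small beside sampling error, but it does not average out.

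The effect is confined to the reported estimate. ORR is secondary and descriptive, and the study's criterion for a promising result in 17.5.2 rests on the T-cell fold change. Nothing here alters the primary endpoint or a go/no-go decision.

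**What to change.** In 17.5.3 item 5:

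- Make the main ORR denominator all infused patients with measurable disease at baseline.
- Count as non-responders those with no documented response assessment in the 90-day evaluation window because of death, deterioration, new therapy or loss to follow-up. A response documented anywhere within that window still counts as a response.
- Report the number of such patients and the reasons.
- Keep the 8.1.1 evaluable set as a sensitivity analysis.
- List uninfused patients, including those who progressed before infusion, separately by reason.

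In the same edit, reconcile the response criterion: Section 2 gives iRECIST for overall response, and 17.5.3 gives RECIST 1.1.

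The cost is wording only. No scans or patients are added, and Section 10.2 already permits record review for progression and survival. The downside is that ORR may come out somewhat lower, and a scan missed for reasons unrelated to disease counts as a failure. The sensitivity analysis shows how much that matters. Settling the rule before the response data are reviewed also removes a later choice between denominators.

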Protocol Title: Duvelisib Exposure to Enhance Immune Profiles of T Cells in Patients with Diffuse Large B Cell Lymphoma (DEEP T CELLS)

Endpoints:	
Primary Endpoint:
 
• The fold increase in the proportion of T cell phenotypes expressing CD 27/28 (to overall T cell count) after 8 to 15 day exposure to duvelisib 
Secondary Endpoints:
 
• The proportion of duvelisib consumed as evaluated by the patient pill diaries.• Manufacturing time of CAR-T 19 cells in weeks (includes manufacturing failure)• The proportion of CD27/28 double positive T cells and CD4/8 double negative T cells• CAR-T kinetics assessment by PCR• Overall response at 90 days after CAR-T cell infusion defined by the Tumor Response Assessment that are complete responders (CR) and partial responders (PR).• Progression-free Survival (PFS) at 90 days per RECIST 1.1 and Overall Survival at 90 days• ICU transfer due to CRS and/or neurotoxicity or due to the treatment with tocilizumab and/or corticosteroids• Grade III-V toxicities (as defined by CTCAE version 5.0)
Study Population:	20 patients will be enrolled with relapsed/refractory DLBCL or relapsed/refractory follicular lymphoma
Phase:	Pilot
Description of Sites/Facilities Enrolling Participants:	This study will be at Winship Cancer Institute, Emory University.
Description of Study Intervention:	Duvelisib is an oral PI3K inhibitor that is given at a dose of 25mg BID prior to manufacturing of CAR-T cells.
Study Duration:	We estimate that the duration of the study will be approximately 18 months.

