1. To evaluate patient compliance with duvelisib. 2. To evaluate the time required for manufacturing CAR-T using mononuclear cells from duvelisib-treated patients. 3. To describe the frequencies of CD27/28 double positive T cells and CD4/8 double negative T cells 4. To evaluate expansion and persistence of CAR-T cells 5. To evaluate overall response rates following CAR-T cell therapy 6. To evaluate survival rates following CAR-T cell therapy 7. To describe the frequency of CRS and neurotoxicity requiring ICU transfer (for CRS or neurotoxicity) and/or treatment 8. Describe the safety and tolerability profile of duvelisib	1. The proportion of duvelisib consumed as documented by the patient on the pill diaries. 2. Manufacturing time of CAR-T 19 cells in weeks (includes manufacturing failure) 3. The proportion of CD27/28 double positive T cells and CD4/8 double negative T cells 4. CAR-T kinetics assessment by PCR 5. Overall response (per iRECIST) at 90 days after CAR-T cell infusion defined by the Tumor Response Assessment that are complete responders (CR) and partial responders (PR). 6. Progression-free Survival (PFS) at 90 days per RECIST 1.1 and Overall Survival at 90 days 7. ICU transfer due to CRS and/or neurotoxicity or due to the treatment with tocilizumab and/or corticosteroids 8. Grade III-V toxicities (as defined by CTCAE version)

3. Background

Diffuse Large B Cell Lymphoma (DLBCL) and relapsed/refractory follicular lymphoma:

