- CAR T phenotyping
- PET/CT or CT (day 90 only post CAR T)

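### Section 8.3 scores best response up to the 90-day scan while the endpoint is response at 90 days; the two ORRs can differ if unscheduled earlier scans are counted

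*Combined protocol and SAP*

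**What the plan says.** **Endpoint.** The synopsis gives the secondary endpoint as "Overall response at 90 days after CAR-T cell infusion defined by the Tumor Response Assessment", counting CR and PR. Section 2 has the same time point: "Overall response (per iRECIST) at 90 days after CAR-T cell infusion". (It names iRECIST where other sections name RECIST 1.1, which is a separate matter.) Sections 8.1 and 8.1.1 agree on timing: re-evaluation, and evaluability for response, are at 3 months after infusion.

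**Section 8.3.** "The best overall response is the best response recorded from the start of the treatment until repeat imaging at 90 days". The next sentence adds: "The patient's best response assignment will depend on the achievement of both measurement and confirmation criteria". The table that follows combines target, non-target and new lesions into an overall response. The footnote to its confirmation entries reads: "Only for non-randomized trials with response as primary endpoint". Section 8.1 opens with "Although response is not the primary endpoint of this trial".

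**Analysis.** 17.5.3 item 5 says: "The ORR (complete response or partial response) will be summarized along with an exact 95% confidence interval". It gives no time point and sends the reader to 8.2 for the response definitions.

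**Scans.** Table 2 in section 1.3 and the post-infusion list in 5.6 schedule one imaging assessment after infusion, at Day 90.

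**The concern.** Response at a fixed time and best response over an interval are different quantities. A patient who responds on an early clinical scan and has progressed by Day 90 is a responder under 8.3 and a non-responder under the endpoint. Item 5 does not choose between them.

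The start of the 8.3 interval is also open. If it is the first duvelisib dose, the interval includes the period after apheresis in which 7.2 allows bridging chemotherapy. A response to bridging could then be scored, although the endpoint concerns response after infusion.

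What is at stake is whether the reported ORR has one pre-specified meaning, and whether patients who happen to have extra scans get extra chances to be counted as responders.

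**Working it through.** The plan gives no expected ORR and no precision target for response, so there is no stated figure to reproduce. The check has three parts.

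**1. Scheduled scan only.** Inputs: one post-infusion scan at Day 90 (1.3 Table 2, 5.6, 8.1), and the footnote to the 8.3 table applied. The best of a single assessment is that assessment, so best response to Day 90 equals response at Day 90. The difference in ORR is 0.

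**2. Earlier unscheduled scans also counted.** Let r be responders at Day 90 and k be patients with a response on an earlier scan that is lost by Day 90.

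- ORR under the endpoint = r/n; ORR under 8.3 = (r + k)/n.
- Shift = k/n. At n = 20 one patient moves ORR by 1/20 = 5 percentage points.
- Exact (Clopper-Pearson) 95% limits for x of n: lower = 2.5% quantile of Beta(x, n − x + 1); upper = 97.5% quantile of Beta(x + 1, n − x).

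The values of r and k are assumptions, and n = 20 is the planned enrolment:

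| r | k | ORR under 8.3 | Exact 95% CI |
|---|---|---|---|
| 10 | 0 | 10/20 = 50% | 27.2–72.8% |
| 10 | 1 | 11/20 = 55% | 31.5–76.9% |
| 10 | 2 | 12/20 = 60% | 36.1–80.9% |
| 10 | 3 | 13/20 = 65% | 40.8–84.6% |
| 10 | 4 | 14/20 = 70% | 45.7–88.1% |

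With r = 8, k from 0 to 4 takes ORR from 40% to 60%. With r = 12 it goes from 60% to 80%. The denominator may be below 20, because 8.1.1 limits response evaluability to patients with measurable disease who were infused and re-evaluated. Each patient would then weigh more than 5 points.

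**3. The confirmation sentence.** The text of 8.3 makes the assignment depend on confirmation. The footnote restricts the confirmation entries to trials with response as primary endpoint, and 8.1 says this is not one. On the plan's own terms the entries do not apply, so the sentence and the footnote contradict each other.

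If the sentence were enforced anyway, the rows would behave differently:

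- The CR/CR row and the row with target CR and non-target disease neither CR nor PD ask for confirmation more than 4 weeks later, which one scan cannot supply.
- The target-PR row asks only for one record more than 4 weeks from baseline, which a Day-90 scan can meet.
- The row with target CR and non-target disease not evaluated shows no confirmation entry in the table as read.

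With an assumed 10 responders of 20 and unconfirmed CRs dropped, ORR would be 50% if none are CR, 5/20 = 25% (8.7–49.1%) if five are, and 0% (0–16.8%) only if all ten are.

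**The case against.** The best counter-argument is that the plan already settles the matter. The Day-90 time point appears in the synopsis, in section 2 and, as 3 months, in 8.1 and 8.1.1. Best overall response is in no endpoint list. Item 5 cites 8.2 and not 8.3. Only one scan is scheduled, and the chart-review list in 7.4 does not mention imaging. ORR carries no test and no decision rule, because the study's criterion for a promising result rests on CD27/CD28 fold change.

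Much of this stands. It shows that the Day-90 reading is the more natural one and that the issue is small. It does not close the gap, for four reasons:

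- Section 8.2 defines CR, PR, SD and PD without an assessment time, and the full lesion-combination table is only in 8.3. Item 6 of 17.5.3 also sends the analyst to 8.3, so that section is in use.
- Follow-up after discharge is by routine practice (7.4), and 17.4 says ORR is captured by chart review. Earlier clinical scans are not excluded.
- 10.2 lists the 90-day tumour assessment for patients who have not started a new antineoplastic regimen. A patient who responds, relapses and is re-treated may have no Day-90 scan, and this is where the two rules part.
- No section says how unscheduled scans count.

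A reader might also infer that best response would conceal early relapse. The documents do not support that: 90-day PFS and CAR-T persistence by PCR are reported separately in 17.5.3.

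**Conclusion.** The inconsistency is real and minor. Section 8.3 states a response rule that does not match the endpoint, leaves its starting point undefined, and contradicts its own footnote on confirmation. Item 5 does not say which rule governs.

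Two stronger readings are tempting and should not be drawn. The first is that ORR must differ according to the text followed. It need not: with the scheduled Day-90 scan alone the difference is zero. A difference requires that unscheduled earlier scans be counted, which the plan leaves possible but does not provide for. The second is that confirmation with one scan drives ORR to 0/20. The footnote with 8.1 disapplies confirmation, and even if it were enforced, the target-PR row can be met at Day 90.

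Where earlier scans do count, the size is 5 percentage points per affected patient at a denominator of 20. Three such patients would take 50% (27–73%) to 65% (41–85%). The responder counts, the number of patients affected and the denominator are all assumptions.

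**What to change.** - **17.5.3 item 5:** define ORR as overall CR or PR at the Day-90 post-infusion assessment. Count patients with documented progression or death before Day 90 as non-responders, and carry this into 8.1.1, which otherwise drops patients who were not re-evaluated.
- **Scan window:** use a single window. Table 2 in 1.3 allows 3 days either side of Day 90 and 8.1.1 allows 2 weeks either side of 3 months; these must be reconciled.
- **8.3:** delete the confirmation sentence and keep the lesion-combination table to classify the Day-90 scan.
- **Best response:** if it is wanted, report it as a separate descriptive item counted from CAR-T infusion, not as the ORR.

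The cost is a few lines of protocol and analysis-plan wording, with no added scans or patients. ORR may read slightly lower than under a best-response rule.
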